### 3. Introduction

#### 3.1. Study Rationale

T-cells play a central role in immune response to tumors. However, tumors have adopted multiple mechanisms to evade host immune surveillance. One of the key mechanisms is programmed cell death protein-1 receptor (PD-1) and its ligands, programmed death ligand 1 (PD-L1) and programmed death ligand 2 (PD-L2), coinhibitory molecules (immune checkpoints) that suppress T-cell-mediated immune responses. Both PD-L1 and PD-L2 ligands can bind to the PD-1 receptor on T-cells.

In addition, PD-L1 can also bind to B7-1 on T-cells. These PD-1 axis interactions lead to suppression of T-cell activation. In a variety of tumors, PD-L1 is frequently over-expressed by tumor cells. Blocking the PD-1/PD-L1 axis has been shown to remove this suppression and reinvigorate T-cell activation (Zou et al. 2016).

While anti-PD-1 and anti-PD-L1 antibodies have demonstrated durable clinical responses in multiple tumor indications, only a subset of patients benefit from these treatments with room for further improvement (Jenkins et al. 2018). Eli Lilly & Company (Lilly) has designed a novel approach using a bispecific antibody (BsAb) to target both PD-L1 and PD-1. Such a BsAb will be capable of blocking all interactions of the PD-1/PD-L1 axis (PD-1 with PD-L1 and PD-L2, B7-1 with PD-L1) whereas anti-PD-1 does not block PD-L1-B7-1 interactions and anti-PD-L1 does not block PD-L2-PD1 interactions. In addition, in vitro experiments have demonstrated that LY3434172 can bridge cells engineered to express PD-1 and those that express PD-L1; the clinical relevance of bridging will be assessed in this study.

The goal of this study is to establish the safety of the PD-1/PD-L1 bsAb as monotherapy in patients with advanced solid tumors. If the product has an acceptable clinical safety profile and shows sufficient activity, additional studies and/or cohorts may be added to determine a safe dose alone or in combination with other anticancer therapies.

#### 3.2. Background

While inhibitors of both PD-1 and PD-L1 have shown clinical activity and manageable safety profiles as monotherapy in a variety of tumor types, their efficacy in various tumor types could potentially be improved (Wu et al. 2015). The possible benefit of targeting the PD-1/PD-L1 pathway with another immune checkpoint inhibitor, which can further augment the response, is an important area of interest.

LY3434172 is a human bsAb (effectorless IgG1-Fc) consisting of two different sets of light and heavy chains. One pair of the heavy-light chain is a human immunoglobulin G1 (IgG1) variant that binds PD-L1 and the other pair is a human IgG1 variant that binds PD-1.

The in vitro and in vivo biological properties of LY3434172 were characterized in nonclinical pharmacology studies. LY3434172 blocks all interactions of the programmed death (PD) axis: PD-1 binding to PD-L1 and PD-L2 ligands, as well as B7-1 binding to PD-L1. In vitro, LY3434172 can bridge a PD-L1 expressing target cell and a PD-1 expressing T-cell to enable

T-cell activation that is superior to parental PD-1 and PD-L1 monoclonal antibodies (mAbs) or their combination. Furthermore, LY3434172 demonstrates *in vivo* antitumor efficacy in humanized mouse model systems. Collectively, LY3434172 fully blocks the PD-1 and PD-L1 axes and more effectively releases immune inhibitory signals to promote T-cell activation and enhance antitumor efficacy.

The toxicity profile of LY3434172 was investigated in cynomolgus monkeys administered intravenous (IV) bolus doses of 0, 30, and 100 mg/kg twice weekly for 1-month (9 doses total; [Table JZEA.5](#)). LY3434172 binds to and antagonizes both human and monkey PD-1 and PD-L1 with similar affinity and potency, establishing cynomolgus monkeys as a pharmacologically-relevant species for toxicity testing.

No mortality or significant clinical signs were observed and all animals survived to scheduled necropsy. LY3434172-related clinical pathology changes at both doses were largely limited to minimal decreases in albumin with minimal to mild increases in globulins, compatible with an acute phase response. LY3434172-related microscopic findings of minimal to marked vascular/perivascular mononuclear cell infiltrates in multiple organs were observed in 14 of 16 animals (7 at 30 mg/kg, 7 at 100 mg/kg). The histological features, spectrum of affected organs, and distribution of microscopic findings at both dose levels were consistent with immune complex deposition secondary to an immune response to LY3434172. Microscopic changes similar in appearance and location have been observed in preclinical studies for other biopharmaceuticals, and have been determined to be the result of an immune response to the therapeutic compound (Rojko et al. 2014). Commonly affected organs included brain, heart, gall bladder, and organs of the reproductive and gastrointestinal tracts – a tissue/organ spectrum which is also compatible with published reports (Heyen et al. 2014; Leach et al. 2014; Rojko et al. 2014; Husar et al. 2017; Kronenberg et al. 2017). Immunohistochemical detection of granular deposits containing LY3434172, endogenous monkey immunoglobulin M (IgM) and immunoglobulin G (IgG), and/or complement C3 at sites of vascular lesions in many of the tissues tested provided definitive evidence of immune complex deposition in development of vascular/ perivascular infiltrates.

These findings are consistent with a Type III hypersensitivity response, which have been described in monkey studies for a number of therapeutic monoclonal antibodies (Heyen et al. 2014; Leach et al. 2014; Rojko et al. 2014; Husar et al. 2017; Kronenberg et al. 2017). Importantly in this case, a high incidence of anti-drug antibody (ADA) in LY3434172-treated animals and detection of granular deposits in affected tissues of representative animals provided robust evidence of immune complex disease. In monkeys, immune complex-related vascular/perivascular inflammation is commonly found in varied organs/tissues such as the gastrointestinal tract, gall bladder, heart, and tissues of the reproductive tract, consistent with the organs affected in this study. Based on historical examples, there is low potential risk for clinical translation of both preclinical immunogenicity (IG) and immune complex-related pathology (Husar et al. 2017; Kronenberg et al. 2017).

No LY3434172-related effects were observed on other standard toxicology endpoints in the study with the exception of heart rate (HR) increases noted in a subset of animals affected by

vasculitis (Table JZEA.5). While transient increases in HR were observed in the light photoperiod, most pronounced changes (with maximal increases ranging up to +23 bpm) were observed during the dark phase of the recording period (100 mg/kg only) on Day 5. By Day 22, HR changes of similar magnitude (with maximal changes up to +39 bpm) were observed at both dose levels, with evidence of a carryover effect during predose recording (+17 to 19 bpm) indicative of a reduced but sustained heart rate effect. No changes in QTc or any waveform abnormalities were noted in any animal on either day.

As the vascular findings were considered adverse to the animals in the study at both 30 mg/kg and 100 mg/kg, a no-observed-adverse-effect level (NOAEL) was not identified for this study. The proposed starting dose of 3 mg every two weeks (Q2W) has a multiple of  $\geq 2,000$ -fold based on dose and projected maximum observed drug concentration ( $C_{max}$ ), and a  $> 10,000$ -fold multiple based on projected average drug concentration ( $C_{av}$ ) over the dose interval, compared to the lowest dose of 30 mg/kg tested in monkeys in the 1-month repeat-dose study.

**Table JZEA.5. Summary of 1-month Repeat-Dose Monkey Toxicity Study with LY3434172**

Study Type	Species	Doses (mg/kg)	Parameters Evaluated	Low Dose e	High Dose e
Study Number	Number	Route	Duration		
1-month GLP toxicity study 20134606	Monkey Cynomolgus 4/sex/group	0 a , 30, 100 IV twice-weekly for 1 month (9 total doses)	Mortality, BW, clin signs, phys, temp, resp, neuro, ophthal, ECG, TK/ADA, immunob b , clin path c , path d	30 mg/kg IV (Exposure Day 29: mean AUC 0-96hr = 103000 $\mu$ g*hr/mL; C 0 =1540 $\mu$ g/mL)	100 mg/kg IV (Exposure Day 29: mean AUC 0-96hr = 400000 $\mu$ g*hr/mL; C 0 =5610 $\mu$ g/mL)
Microscopic findings:	LY3434172-related adverse findings included minimal to marked vascular/perivascular mononuclear or mixed cell infiltrates in 14 of 16 animals (7 animals at 30 mg/kg, 7 animals at 100 mg/kg). The histological nature, tissue locations, and distribution of the lesions were consistent with an indirect ADA response to LY3434172 and resultant immune complex deposition and damage. Subsequent investigative work demonstrated immune complex deposition in lesions from multiple tissues/ organs from a representative subset of affected animals				
Cardio-vascular findings:	Increases in heart rate (HR) were observed in several animals on Day 5 (100 mg/kg; up to +23 bpm) and Day 22 (30 and 100 mg/kg; up to +39 bpm), most notably pronounced during the dark photoperiod. Changes on Day 22 were elevated at predose (+17-19 bpm) and were of a similar magnitude in both dose groups during the dark photoperiod.				

Abbreviations: ADA = anti-drug antibody; mean AUC0-96hr = average area under the plasma concentration-time curve from time zero to 96 hours for both males and females; BW = body weight; clin = clinical; mean C0 = mean maximal plasma concentration for both males and females extrapolated to t=0 time point; ECG = electrocardiogram; immuno = immunophenotyping; IV = intravenous; neuro = neurological evaluations; NOAEL = no-observed-adverse-effect level; NK = natural killer; ophthal = ophthalmic examinations; path = pathology; phys = physical examinations; resp = respiratory rate and depth; temp = body temperature; TK = toxicokinetics (plasma LY3434172).

a Vehicle control group.

b Peripheral blood immunophenotyping.

c Hematology, coagulation, cytokines, complement, clinical chemistry, and urinalysis.

d Organ weights, gross pathology, histopathology, immunohistochemistry.

e An NOAEL was not identified in this study due to indirect adverse effects in animals that were driven by an immune response to LY3434172.

Additional information pertaining to nonclinical efficacy and safety may be found in Section 4.2 of the Investigator's Brochure (IB).

Information pertaining to nonclinical pharmacokinetics (PK) and metabolism may be found in Section 4.1 of the IB.

### 3.3. Benefit/Risk Assessment

More information about the known and expected benefits, risks, serious adverse events (SAEs) and reasonably anticipated adverse events (AEs) of LY3434172 are to be found in the Investigator's Brochure (IB).

## 4. Objectives and Endpoints

Table JZEA.6 shows the objectives and endpoints of the study.

**Table JZEA.6. Objectives and Endpoints**

Objectives	Endpoints
Primary	
To assess the safety and tolerability of LY3434172, thereby identifying a RP2D of LY3434172, administered to patients with advanced solid tumors.	
 
• DLTs
 
• Safety (including but not limited to): TEAEs, DLT-equivalent toxicities, SAEs, deaths, and clinical laboratory abnormalities per CTCAE (Version 5.0)
 

Secondary	
To assess the PK in patients with solid tumors of LY3434172.	
 
• AUC, <math>C_{\min}</math> and approximate <math>C_{\max}</math> of LY3434172
 

To assess preliminary antitumor activity a of LY3434172	
 
• ORR
 
• DOR
 
• TTR
 
• DCR
 

Tertiary/Exploratory	
To characterize tumor tissue and blood biomarkers relevant to LY3434172, including but not limited to immune cells/immune functioning, mechanism of action of study drugs, cancer-related pathways, and disease state	
 
• Results of biomarker analyses
 
• Clinical outcomes
 

To explore the association between biomarkers and dose, concentrations and clinical outcomes	
 
• Results of biomarker analyses
 
• Clinical outcomes
 

To assess the IG of LY3434172 in patients with advanced solid tumors.	
 
• Relationship between TE ADA and safety
 
• Relationship between TE ADA and LY3434172 pharmacokinetics.
 

To assess PFS and OS of patients receiving LY3434172.	
 
• PFS
 
• OS
 

Abbreviations:  $C_{\max}$  = maximum serum/plasma concentration;  $C_{\min}$  = minimum serum/plasma concentration; CTCAE = Common Terminology Criteria in Adverse Events; DCR = disease control rate; DLT = dose-limiting toxicity; DOR = duration of response; IG = immunogenicity; ORR = objective response rate; OS = overall survival; PFS = progression-free survival; RECIST = Response Evaluation Criteria in Solid Tumors; RP2D = recommended Phase 2 dose; SAE = serious adverse event; TEAE = treatment-emergent adverse event; TE ADA = Treatment-emergent anti-drug antibodies; TTR = time-to-response.

a Response assessment using RECIST 1.1 and RECIST 1.1 with confirmatory scan for disease progression.

## 5. Study Design

### 5.1. Overall Design

Study J1E-MC-JZEA (JZEA) is a multicenter, nonrandomized, open-label, first in human Phase 1 study in patients with advanced solid tumors.

Phase 1 study will assess the safety and tolerability of LY3434172, administered as a monotherapy in patients with select advanced solid tumors (see [Figure JZEA.1](#)). LY3434172 will be administered as an IV bolus injection for doses less than 100 mg (approximately 5 to 10 minutes) and for doses  $\geq$ 100 mg, IV infusion over approximately 60 minutes. Patients enrolled into Cohorts A1 through A5/6 will be administered LY3434172 on a Q2W dose schedule. Cohort A6 is an optional cohort that may be explored at a dose not exceeding 1000 mg of LY3434172 based on safety, PK, and pharmacodynamic data. Dose escalation will be driven by modified toxicity probability interval 2 (mTPI2) method (Guo et al. 2017), enrolling at least three patients per cohort. Further discussion on dose escalation is explained in Section [5.1.1](#).

To facilitate a thorough safety evaluation and exploration of PK and pharmacodynamics effects of the every two week (Q2W) dosing schedule (Cohorts A1 to A6) will be explored. Once dose-limiting toxicity (DLT) period is completed for respective Cohorts A1 to A5/6 up to approximately 12 to 15 additional patients may be added to two dose levels selected from these cohorts (see [Figure JZEA.1](#)). After evaluating PK/pharmacodynamic data from these cohorts, any doses from the dose escalation range could be used in order to cover the entire predicted biologically effective dose (BED) and allow for uncertainty around it (see Section 5.5). For example, if 300 mg is a dose level selected, additional patients may be enrolled in parallel with Cohort A5 after Cohort A4 has cleared DLT.

In addition, an every three-week (Q3W) dosing schedule (Cohorts A7 and A8) will be evaluated to allow for flexibility for future combinations with standard-of-care agents that may use a Q3W dose regimen. The Q3W dosing schedule could be initiated as Cohorts A7 and A8 in parallel with the enrollment of additional patients enrolled into two dose levels of the Q2W schedule, respectively.

Ongoing safety reviews between the Lilly and the investigators will be conducted after completion of the DLT period for each cohort to ensure it is safe to continue with the next dose-escalation cohort.

Interim analyses will be conducted at the end of dose escalation from Cohorts A1 to A5/6 at completion of DLT period across these cohorts. The recommended Phase 2 dose (RP2D) will be identified after final analyses upon completion of this Phase 1 study. If LY3434172 has an acceptable clinical safety profile and shows sufficient activity, additional studies and/or cohorts may be added to determine a safe dose alone or in combination with other anticancer therapies. As noted in Section [9.8](#), PD-L1 expression and other biomarkers will be evaluated, and may influence enrichment strategies for subsequent studies and/or cohorts.

CCI

CCI

### 5.1.1. Dose Escalation

The first patient will be enrolled in Cohort A1 and treated according to a Q2W dosing regimen (see [Figure JZEA.1](#)). CCI

A DLT

observation period of 28 days (42 days in Cohort A1) will apply to all patients on the Q2W dosing regimen in subsequent cohorts. Ongoing safety reviews between the Lilly clinical research physician/clinical research scientist (CRP/CRS) and the investigators will be conducted during and upon completion of the DLT period for each cohort, to ensure it is safe to continue with the next dose-escalation cohort.

After the first patient in Cohort A1 receives the first dose of LY3434172, there will be a delay of 1 week before the second patient receives LY3434172 to allow for safety observation. In all subsequent cohorts, the first patient in each dose level will be observed for approximately 24 hours before any additional patients are treated; no additional delays are required for subsequent patients in the same cohort.

Patients in Cohorts A2, A3, A4, A5, and A6 (optional), respectively, CCI provided safety is established in the preceding cohorts. Once DLT period of 28 days for Q2W, except Cohort A1 with 42 day DLT, is completed for respective dose levels within Cohorts A1 to A5/A6, two dose

levels, yet to be determined but will be selected from these cohorts, can be expanded between 12 and 15 patients in total. Pharmacokinetic, pharmacodynamic and safety data evaluated during the course of the dose escalation will be used to select these two dose levels. The purpose of expanding to additional 12-15 patients is to further inform safety, PK and pharmacodynamics. These cohorts will continue to enroll while interim analysis (IA) is ongoing.

Cohorts of patients will be treated with escalating doses of LY3434172 according to an mTPI-2 method until the criteria for reaching the maximum-tolerated dose (MTD) are met. For some immuno-oncology compounds that have manageable safety profiles and do not reach a MTD, additional information such as pharmacodynamic markers may be helpful in determining the appropriate RP2D (Agrawal et al. 2016; Parchment et al. 2016).

A Q3W dosing regimen will be explored in Cohorts A7, A8 at doses yet to be determined. The Q3W dosing regimen will use the LY3434172 dose anticipated to have drug exposure similar to two selected Q2W dose levels where additional patients were enrolled. The Q3W dosing schedule could be initiated as Cohorts A7 and A8 in parallel with the Q2W expansion respectively.

## 5.2. Number of Patients

Enrollment in each cohort will be adjusted if needed to allow adequate assessment of safety and preliminary antitumor activity at the LY3434172 RP2D. Planned enrollment is as follows:

Approximately 15 to 20 patients will be enrolled in Q2W dose escalation, approximately 12 to 15 additional patients may be added to two dose levels selected from Cohorts A1 to A5/A6 after selected dose level has cleared the DLT period for adequate assessment of safety and exploration of PK and pharmacodynamic effects. The additional patients for the two selected dose levels can be enrolled in parallel to dose escalation in Q2W as long as the dose level explored has cleared DLT. In parallel, patients will be enrolled in Q3W cohorts (A7 and A8) to allow flexibility for future combinations with standard-of-care agents. The sample size of Q3W depends primarily on PK profiles and clinical considerations. A minimum of three patients will be enrolled in each cohort.

## 5.3. End of Study Definition

End of the study is the date of the last visit or last scheduled procedure shown in the Schedule of Activities (Section 2) for the last patient.

## 5.4. Scientific Rationale for Study Design

See Sections 3.1 and 3.3.

CCI

CCI

## 6. Study Population

Prospective approval of protocol deviations to recruitment and enrollment criteria, also known as protocol waivers or exemptions, are not permitted.

### 6.1. Inclusion Criteria

Patients are eligible to be included in the study only if they meet all the following criteria:

- [1] Melanoma, NSCLC, squamous cell carcinoma of the head and neck (SCCHN), urothelial cancer, gastric cancer, colorectal cancer, biliary tract cancer, anal cancer, nasopharyngeal cancer, esophageal cancer, SCLC, ovarian cancer, mesothelioma, pan-tumor MSIhi solid tumors, hepatocellular carcinoma, merkel cell cancer, cutaneous squamous cell carcinoma, endometrial cancer, breast cancer, cervical cancer, thyroid cancer, salivary cancer, and prostate cancer who have received at least one line of standard systemic therapy for their respective tumor type in the metastatic setting with progressive locally advanced or metastatic disease and that is not amenable/resistant to approved standard-of-care therapy. Prior anti-PD-1 and anti-PD-L1 allowed if they received another therapy immediately prior to this study or there has been a lapse of approximately  $\geq 90$  days from prior therapy. If patients received prior anti-PD-1 or anti-PD-L1, the following criteria need to be met:
  - a) did not experience a toxicity that led to permanent discontinuation of prior anti-PD-1, anti-PD-L1, or other immunotherapy.
  - b) have completely recovered to at least his or her previous baseline level prior to screening from any clinically significant AEs that occurred during prior immunotherapy.
  - c) did not experience any of the following irAEs during prior anti-PD-1, anti-PD-L1, or other immunotherapy:
    - a Grade  $\geq 3$  irAE
    - any grade neurologic or ocular irAE
    - any grade immune-related pneumonitis or cardiomyopathy
  - d) did not require immunosuppressive agents, other than corticosteroids for the management of an AE, did not experience recurrence of a Grade  $\geq 3$  AE if rechallenged, and does not currently require maintenance doses of  $>10$  mg prednisone (or equivalent) per day.
- [2] have at least one measurable lesion assessable using standard techniques by Response Evaluation Criteria in Solid Tumors Version 1.1 (RECIST 1.1) (Eisenhauer et al. 2009). Bone metastases are not considered measurable.

- [3] are able and willing to provide the protocol required biopsies from a newly obtained core or excisional pre-treatment biopsy of a tumor lesion and a newly obtained core or excisional biopsy collected during the study treatment period (See Section 9.8.1). (Note: An archived tumor sample also will be requested, if not restricted by local regulations).
- [4] have an Eastern Cooperative Oncology Group performance status of 0 or 1 (Oken et al. 1982).
- [5] have discontinued all previous treatments for cancer for at least 14 days and recovered from the acute effects of therapy. Patients must have discontinued from previous treatments, as shown below:

Previous Treatments	Length of Time Prior to First Dose of Study Treatment
Cytotoxic therapies or targeted agents that are small-molecule inhibitors	≥14 days
Mitomycin-C or nitrosoureas	>42 days
Biologic agents (excludes anti-PD-1, anti-PD-L1)	≥14 days
Radiotherapy	≥28 days
Limited field radiotherapy (i.e. <25% bone marrow affected)	≥14 days
Major surgery, excluding biopsy	Patients with recent major surgery must have recovered, in the opinion of the investigator, from the toxicity and/or complications from the intervention before starting therapy.

a At the discretion of the investigator, patients with hormone-refractory prostate cancer who are stable on gonadotropin-releasing hormone agonist therapy and patients with breast cancer who are stable on antiestrogen therapy (for example, an aromatase inhibitor) may continue that treatment while enrolled in this study.

- [6] have adequate organ function, as defined below, with all screening laboratory assessments performed within 28 days of treatment initiation.

System	Laboratory Value
Hematologic	
ANC	≥1.5 × 10  cells/L
Platelets	≥100 × 10  /L
Hemoglobin	≥9 g/dL  At the discretion of the investigator, patients may receive erythrocyte transfusions to achieve this hemoglobin level; however, study treatment may not begin until 2 days after erythrocyte transfusion and after confirmation of hemoglobin ≥9 g/dL.
aPTT	≤1.5 × ULN

Hepatic	
Total bilirubin	$\leq 1.5 \times \text{ULN}$ OR $< 3.0 \times \text{ULN}$ for patients who have Gilbert's syndrome
ALT and AST	$\leq 2.5 \times \text{ULN}$ OR $\leq 5 \times \text{ULN}$ if the liver has tumor involvement
Renal	
Serum creatinine OR Calculated creatinine clearance	$\leq 1.5 \times \text{ULN}$ OR $\geq 50 \text{ mL/min}$

Abbreviations: ALT = alanine aminotransferase; ANC = absolute neutrophil count; aPTT = activated partial thromboplastin time; AST = aspartate aminotransferase; HCC = hepatocellular carcinoma; ULN = upper limit of normal.

Note: Adequate organ function should be confirmed within 7 days prior to first dose on Cycle 1 Day 1.

- [7] are, at the time of screening,  $\geq 18$  years old or of an acceptable age to provide informed consent according to local regulations, whichever is older
- [8] Men with partners of childbearing potential or women with childbearing potential must agree to use a highly effective contraceptive method of birth control ([Appendix 1](#)) during study treatment and for at least 6 months following the last dose of study drug.
- [9] Women of childbearing potential must have a negative serum pregnancy test documented within 7 days prior to initiation of treatment (see [Appendix 9](#)).
- [10] have given written informed consent/assent prior to any study-specific procedures
- [11] have an estimated life expectancy of  $\geq 12$  weeks, in the judgment of the investigator
- [12] are reliable and willing to make themselves available for the duration of the study and are willing to follow study procedures

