[15] Have symptomatic central nervous system (CNS) malignancy or metastasis (screening not required). Patients with treated CNS metastases are eligible for this study if they are not currently receiving corticosteroids and/or anticonvulsants to treat CNS metastases, and their disease is asymptomatic and radiographically stable for at least 30 days.

[16] Unresolved toxicities from prior anticancer therapy, including immune-related adverse event (irAE), that have not resolved to the baseline levels prior to starting the prior anticancer therapy.

[17] have received a live vaccine within 30 days before the first dose of study treatment. Examples of live vaccines include, but are not limited to, the following: measles, mumps, rubella, chicken pox, yellow fever, rabies, *Bacillus Calmette–Guérin*, and typhoid vaccine. Seasonal influenza vaccines for injection are generally killed virus vaccines and are allowed; however, intranasal influenza vaccines (for example, FluMist®) are live attenuated vaccines and are not allowed.

[18] are pregnant, breastfeeding, or planning to become pregnant during the study or within 6 months of the last dose of LY3434172.

[19] have a history or current evidence of any condition, therapy, or laboratory abnormality that might confound the results of the study, interfere with the patient's participation for the full duration of the study, or is not in the best interest of the patient to participate, in the opinion of the treating investigator

[20] have current or history of allergy or hypersensitivity to study drug components

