#### **7.2.2.2.1. Events That Are Not Considered to Be DLTs**

**The following events will not be considered to be DLTs:**

- Toxicity that is clearly and directly related to the primary disease or to another etiology
- Grade 3 endocrine disorder (thyroid, pituitary, and/or adrenal insufficiency), if both the following criteria are met:
  - the disorder is manageable with or without systemic corticosteroid therapy and/or hormone replacement therapy, and
  - the patient is asymptomatic
- Grade 3 inflammatory reaction attributed to a local antitumor response (such as, inflammatory reaction in the lymph nodes or at sites of metastatic disease)
- Any grade vitiligo or alopecia
- First occurrence of Grade 3 infusion-related reaction (IRR) during infusion of LY3434172, if both of the following criteria are met:
  - the patient did not receive corticosteroid prophylaxis, and
  - the Grade 3 IRR resolves within 6 hours with appropriate clinical management
  - If symptoms reappear, the event would be considered a DLT.
  - If this first occurrence is anaphylaxis of any grade, the event would be considered a DLT.
- Grade 3 or 4 neutropenia meeting both of the following criteria are met:
  - is not associated with fever or systemic infection, and
  - improves by at least 1 grade within 7 days
- Grade 3 or 4 lymphopenia

It should be recognized that for patients who have received prior immune therapy, including checkpoint inhibitor therapy, there is the potential for delayed manifestation of serious irAEs such as colitis, hepatitis, pneumonitis, and endocrinopathies. Patients manifesting potential delayed irAEs should receive prompt evaluation and treatment.

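### Inclusion [1] checks immune-toxicity history only after prior anti-PD-1/PD-L1, though its sub-criteria name other immunotherapy; some resolved severe irAEs on other classes therefore meet no objective bar

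*Protocol*

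**What the plan says.** Inclusion [1] in Protocol Section 6.1 allows prior anti-PD-1 and anti-PD-L1 treatment subject to a timing rule. It then introduces four sub-criteria with the words "If patients received prior anti-PD-1 or anti-PD-L1, the following criteria need to be met".

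- (a) requires that the patient "did not experience a toxicity that led to permanent discontinuation of prior anti-PD-1, anti-PD-L1, or other immunotherapy".
- (b) requires recovery from "clinically significant AEs that occurred during prior immunotherapy".
- (c) requires that the patient "did not experience any of the following irAEs during prior anti-PD-1, anti-PD-L1, or other immunotherapy". The list is any Grade 3 or higher irAE, neurologic or ocular irAEs of any grade, and immune-related pneumonitis or cardiomyopathy of any grade.
- (d) rules out past need for non-steroid immunosuppression to manage an adverse event, recurrence of a Grade 3 or higher event on rechallenge, and a current steroid requirement above 10 mg/day of prednisone.

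Inclusion [5] admits patients with other prior biologics. Its washout row reads "Biologic agents (excludes anti-PD-1, anti-PD-L1") and asks for at least 14 days. The stem of [5] adds recovery from acute effects.

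Exclusion [16] in Section 6.2 concerns "Unresolved toxicities from prior anticancer therapy, including immune-related adverse event (irAE), that have not resolved to the baseline levels".

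Section 7.2.2.2.1 says of patients with any prior immune therapy, checkpoint inhibitors included, that "there is the potential for delayed manifestation of serious irAEs such as colitis, hepatitis, pneumonitis, and endocrinopathies".

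**The concern.** The condition that switches on (a)-(d) is narrower than the sub-criteria themselves. The words about other immunotherapy take effect only for someone who has also had anti-PD-1 or anti-PD-L1. A patient treated with another class alone never reaches them, whatever the toxicity was.

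This matters because the study is first-in-human (Section 5.1), and Section 7.4 expects immune-related events from the drug's mechanism. Section 6 rules out waivers, so sites work to the written wording. Two things are at stake. One is the safety of patients who have already had serious immune toxicity. The other is how a DLT-type irAE in such a patient is read in a cohort that may hold only three people (Section 7.2.2.1).

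**Working it through.** No figure in the plan depends on this, so the check is textual. Take a patient whose only immunotherapy was neither anti-PD-1 nor anti-PD-L1. For each history that (a)-(d) treat as disqualifying, ask which other criterion applies.

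| History named in (a)-(d) | Other rule that reaches it | Objective bar once resolved? |
|---|---|---|
| (a) Permanent discontinuation for toxicity | None in [5], [6], [14] or [16] as such | No |
| (b) Incomplete recovery | [16]; [5] for acute effects | Not applicable: largely covered while unresolved |
| (c) Grade 3 or higher irAE | [14](f) autoimmune disease and vasculitis-type history; [14](h) inflammatory enteropathy; [14](i) steroid-treated pneumonitis; [14](j) cardiovascular disease | Partly; not for hepatic, renal or skin events in general |
| (c) Neurologic or ocular irAE, any grade | [16] while unresolved | No |
| (c) Pneumonitis or cardiomyopathy, any grade | [14](i) and [14](j), within their own limits | Partly |
| (d) Past non-steroid immunosuppression | [14](g) addresses use, not past need | No |
| (d) Grade 3 or higher recurrence on rechallenge | None as such | No |
| (d) Current steroid above 10 mg/day | [14](g) | Covered |

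Inclusion [6] sets laboratory limits at screening. It tests present organ function and is silent on past events. Exclusion [19] allows the investigator to exclude on any history, but by judgement.

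**The same toxicity treated two ways.** Patients X and Y each had a Grade 3 skin irAE on the same agent of another class, and each has recovered fully. X also had an anti-PD-1 antibody at some other time without incident. For X the lead-in is met, and (c) excludes because it covers irAEs on other immunotherapy. For Y the lead-in is not met, so (c) is never asked. The event, the agent and the recovery are identical, and the documents give no reason for the difference.

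**What one patient could do to a dose decision.** In Appendix 8, column 3, 0 DLTs gives E, 1 gives S and 2 gives D. One added DLT in a three-patient cohort would therefore move E to S, or S to D. Whether it is added turns on attribution. Section 7.6.1.1 lets a patient be declared non-evaluable when an event meeting DLT criteria is judged most likely due to a prior line of immune therapy, and such patients may be replaced. An event attributed to the study drug still counts.

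**The case against.** The strongest reply is that the lead-in means what it says. A closer history check for patients already exposed to the drug's own pathway is a coherent choice. On that reading the reference to other immunotherapy is not surplus: it extends the check to everything else those patients received. This is grammatically possible and cannot be ruled out. But no rationale for it is given, and the warning in Section 7.2.2.2.1 is not confined to anti-PD-1/PD-L1.

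The second reply is that other criteria do much of the work. That stands in part, as the table shows: unresolved toxicity, current immunosuppression, bowel inflammation and steroid-treated pneumonitis are covered, and [19] could be used in any of the remaining cases. It does not supply an objective bar for those cases.

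Third, the warning in Section 7.2.2.2.1 is about late manifestations of earlier therapy. It does not say that a resolved irAE on another class raises the risk on LY3434172, and no figure in the documents supports that step. This stands, and it limits how far the safety argument can be pressed.

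A reader might infer that any patient with severe irAEs on another immunotherapy is eligible. The documents do not support that, because [14], [16] and [19] still apply. Nor do they show that the sponsor meant (a)-(d) to keep these patients out; that intent is stated nowhere.

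**Conclusion.** The lead-in and sub-criteria of inclusion [1] do not match in scope, and the mismatch leaves a real but limited gap. It concerns patients whose only immunotherapy was of another class, whose toxicity has resolved, and whose history falls outside the conditions in [14]. For them, a resolved hepatic, renal, skin, neurologic or ocular irAE of the kind (c) names, a permanent discontinuation for toxicity, or past non-steroid immunosuppression is left to the investigator's discretion.

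The size cannot be computed. The documents give neither the share of patients with only other-class immunotherapy nor the share of those with a disqualifying event. A reader might multiply planned enrolment by an assumed share. That would have no basis in the documents and would count patients who never had an irAE. The number is probably small. A reader might also expect inflated DLT counts, but the non-evaluability rule makes a shift in the dose decision possible, not predicted.

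The conclusion rests on reading the lead-in literally. It merits correction because it bears on patient safety and is cheap to settle; it does not affect sample size or analysis.

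**What to change.** Reconcile the lead-in of inclusion [1] with (a)-(d). The version consistent with the sub-criteria adds other immunotherapy to the two classes in the condition and leaves (a)-(d) as they are. Since Appendix 1 does not define immunotherapy, a definition should be added so that the wider condition does not take in agents the sponsor did not intend.

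If the sponsor wants the narrower scope, the protocol should say so explicitly, explain why (a)-(c) mention other immunotherapy, and justify leaving the remaining histories to [19]. That choice is the sponsor's.

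Either route is a short wording amendment. The cost of the wider condition is that a very small number of patients with earlier severe irAEs on other immunotherapy could no longer enrol.
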